1. INTRODUCTION

1.1 Background

Approximately 400000 people in the UK have T1D (1). Self-management of T1D involves a challenging regimen requiring monitoring of blood glucose levels several times per day and multiple daily insulin injections. People living with T1D can experience a number of psychological difficulties, including feeling burned out, fear of high and low blood glucose levels, adjustment to diabetes-related complications, and problems around eating. Higher levels of diabetes-related distress are associated with a higher HbA1c (2,3) which is associated with increased risk of micro- and macro vascular diabetes-specific complications. The importance of psychological support for people with T1D is increasingly recognised (4), and both published and Imperial data demonstrate the importance of psychological support (5,6).

Published data describe the assessment and consequences of fear of hypoglycaemia in people with T1D (7,8). Hypoglycaemia fear is associated with a higher HbA1c and increased risk of diabetes-related complications. The Hypoglycaemia Fear Survey (HFS-ii) (9,10) is a valid and reliable tool for assessment used in routine clinical care, including in the psychological assessment and intervention outcome data for the Imperial T1D Psychology service. NICE guidelines (11) reference fear of hypoglycaemia as a barrier to achieving HbA1c targets and recommend continuous glucose monitoring for those with extreme fear.

There is, however, little research about fear, or problematic avoidance, of hyperglycaemia in T1D (12). It is, however, a problem that we see in the T1D clinics at Imperial, often with significant adverse consequences. As well as high levels of distress, it is associated with recurrent hypoglycaemia exposure, eroded hypoglycaemia awareness and increased healthcare utilisation (13). More problematically, fear of hyperglycaemia may not be identified, as the HbA1c is often at, or below, target.

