2. STUDY OBJECTIVES

Primary Objective

Assess how problematic fear of hyperglycaemia is in T1D

Secondary Objectives

Identify whether fear of hyperglycaemia is associated with any clinical factors

Identify the psychological factors that underpin fear of hyperglycaemia

Assess how fear of hyperglycaemia affects self-management of T1D

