3.1 Study Outcome Measures

1. Quantitative data:

- a. Hyperglycaemia avoidance scale (HAS)
- b. Hypoglycaemia fear survey (HFS-II)
- c. Problem areas in diabetes scale 5 (PAID-5)
- d. Patient health questionnaire (PHQ-9)
- e. Generalised anxiety disorder scale (GAD-7)
- f. State trait anxiety inventory (Trait subscale)

2. Descriptive data – semi-structured interview

Additional baseline participant data to be pulled from Cerner/via participant survey:

- Age
- Ethnicity
- Length of diabetes
- Current diabetes treatment
- Diabetes complications: nephropathy, neuropathy, retinopathy, cardiovascular disease
- Recent HbA1C
- Other medical conditions
- Other medications
- Hypos – frequency/severity
- Blood glucose monitoring - method and frequency

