4. PARTICIPANT ENTRY

4.1 Pre-registration evaluations

Potential participants will be identified by the clinical diabetes team from the list of people who attend the diabetes clinics at Imperial College Healthcare NHS Trust. Participants with type 1 diabetes who do not attend an Imperial College Healthcare NHS Trust diabetes clinic who have consented to be contacted by the Imperial diabetes research team for research purposes will also be invited to participate in the study.

Of the participants who are enrolled in the study, and who have consented to be contacted for an interview, the research team plans to select approximately 16 participants to take part in the qualitative interview. Participants will be selected based on clinician identification and participant self-identification of fear of hyperglycaemia, as well as from a dynamic list of those in the upper quadrant of recorded scores on the Hyperglycaemia Avoidance Scale.

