6. ASSESSMENT AND FOLLOW-UP

The main study will consist of completing a survey and some questionnaires. This should take no more than 1 hour to complete by the participant at a time and location convenient to them. Participants will be invited to consent to be contacted for the optional sub-study which will be described later in this section.

All eligible participants will be identified by the clinical care team. A list of potential participants will be identified from the database of all people who attend the diabetes clinics at Imperial College Healthcare NHS Trust (subsequently known as the participant database). Additionally, eligible participants from the list of non-Imperial research consenters will also be contacted about the study.

Potential participants will be contacted in one of three ways by the clinical team:

- a) Participants whose emails are available on Cerner or who are not Imperial patients but have consented to contact for research will be contacted by email by a member of the research team. The email will include the PIS and a link to Qualtrics (an online data collection platform which is supported by the college). Informed consent will be taken via this platform with questionnaires to follow (only accessible if participant has consented to all clauses and signed electronically). Participants will be able to arrange a phone call with the research team to discuss any issues or concerns before signing the consent if they wish. Participants who attend clinics at Imperial College Healthcare NHS Trust will be provided with a unique code to enable researchers to link their questionnaire data with their medical records. This will be different to the study code and which will be assigned to participants after consent in order of enrolment.
- b) For potential participants whose emails are not available or who prefer a hard copy approach, study packs, including the patient information sheet, consent form and questionnaire will be sent by post for completion at home, and returned in a pre-paid addressed envelope to the research team.
- c) Patients who are seen in clinic by the diabetes team will be approached by their clinical team about participating in the study. Those who are interested will then be provided with a consent form and study questionnaire which can either be completed and returned to the research team whilst in the clinic or taken home and returned in a stamped addressed envelope at the participant's convenience.

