Of the participants who are enrolled in the study, and who have consented to be contacted for an interview, the research team plans to select approximately 16 participants to take part in the qualitative interview. Participants will be selected based on clinician identification and participant self-identification of fear of hyperglycaemia, as well as from a dynamic list of those in the upper quadrant of recorded scores on the Hyperglycaemia Avoidance Scale.

Participants will be advised that questionnaires should be returned by the end of the study for inclusion in the study analysis.

Within the patient information sheet there will be contact details for the research team, should the participant wish to discuss the study and obtain any further details.

Once returned, the pseudonymised questionnaire data will be recorded in a password encrypted database on an Imperial College Healthcare NHS Trust or Imperial College London computer (subsequently known as the results database). Informed consent will be filed in the trial master file.

Once informed consent has been provided, the research team will then review the electronic health records of those Imperial College Healthcare NHS Trust participants who have consented to record biochemical data, medical history. Other baseline data e.g. demographics will be collected via a participant survey which will be mailed alongside questionnaires. This data will be recorded in pseudonymised form in the results database. Data from Qualtrics will be downloaded in a PDF format on either an ICL or ICHT computer and printed for hard copy records. Questionnaire scoring data will be pulled from Qualtrics in a pseudonymised format and saved on either an ICL or ICHT computer within an encrypted, password protected document.

In all cases, no samples are taken and all data will be pseudonymised. No follow up outside of usual care will be provided.

If participants wish to see their questionnaire scores, they will be able to request this. They will be sent a standardised letter including their scores on each measure and, where available, what this score is suggestive of (e.g. mild depression). Some of the measures do not have standardised cut-offs. This will only be sent if requested and not for all participants.

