Any participant who scores in the severe range on the GAD-7 (scores of 15-21) or the PHQ-9 (scores of 20-27), or who scores 3 on question 9 of the PHQ-9 (this question relates to thoughts of harm to self) will have a letter sent to their GP advising them of this, and the participant will receive a copy.

Any disclosure made to the researchers that constitutes a safeguarding issue, or a potential risk to self or others, will be shared with the clinical team and managed appropriately as per the usual clinical care pathway, including contacting other agencies where indicated. Where participants report mental health problems such as anxiety or depression, based on the Clinical Psychologist's judgement, they will be signposted or, where appropriate, referred, to appropriate mental health services as is usual practice in their clinical care. This might include, for example: their local mental health trust's Single Point of Access; Improving Access to Psychological Therapies (IAPT); the London-wide Type 1 Disordered Eating Service.

If the participant raises concerns that they do not wish to be shared with their clinical care team, but the researcher feels should be shared, an anonymised discussion will be initiated with the Principal Investigator, and if appropriate, the clinical care team. The Trust Ethics Committee can also be consulted, if appropriate, to consider what is in the participant's best interests.

Participants' GPs will not be informed of their participation in the study as it will not affect their care.

End of study will be defined as last subject last visit (LSV).

Sub-study – Qualitative semi-structured interview

Of the participants who are enrolled into the study (and who have consented to be contacted for an interview) the research team plan to select approximately 16 whose HAS scores are relatively higher than other participants in order to conduct a qualitative semi-structured interview. This will be judged from previous research and participants who score in the upper quartile of the entire measure. (Singh *et al.*, 2014). Participants of varying backgrounds will be selected to ensure a mix of demographics, diabetes duration, HbA1c etc. This is in order to ensure a heterogeneous pool of participants to inform our hypothesis.

Participants will not be reconsented to take part in the interview study as they will have already opted in on the original consent form, having read the PIS which details this sub study. The

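### Does the plan need changing because it names no HbA1c source for non-Imperial participants and lists no item on hypoglycaemia awareness or healthcare use?

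*Combined protocol and SAP*

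**What the plan says.** Section 3.1 puts the baseline items, including recent HbA1c, complications, and frequency and severity of hypos, under one source line: "Additional baseline participant data to be pulled from Cerner/via participant survey". It does not divide them by item or by recruitment group.

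Section 6 divides them further. For Imperial patients the team will "review the electronic health records of those Imperial College Healthcare NHS Trust participants who have consented to record biochemical data, medical history"; other baseline data, with demographics as the example, come from the survey. People attending Imperial clinics "will be provided with a unique code to enable researchers to link their questionnaire data with their medical records". Nobody is tested for the study: "In all cases, no samples are taken".

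Section 4.1 widens recruitment: "Participants with type 1 diabetes who do not attend an Imperial College Healthcare NHS Trust diabetes clinic" are also invited if they have agreed to research contact. No record review is described for them.

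The first secondary objective in Section 2 is to "Identify whether fear of hyperglycaemia is associated with any clinical factors". HbA1c also helps to vary the interview sample: "Participants of varying backgrounds will be selected to ensure a mix of demographics, diabetes duration, HbA1c etc".

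Section 1.1 says of the problem that, besides high distress, "it is associated with recurrent hypoglycaemia exposure, eroded hypoglycaemia awareness and increased healthcare utilisation".

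**The concern.** Two things look wrong at first.

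**Source of HbA1c and complications.** Record review covers consenting Imperial participants only. If the survey carries just the remaining items, as a literal reading of Section 6 suggests, non-Imperial participants would have no HbA1c or complications data. If the survey does ask, their values are self-reported while Imperial values come from records. Data source would then coincide with recruitment group, and an association between avoidance of hyperglycaemia and HbA1c could partly reflect where people were recruited. This bears on the clinical-factors objective, and Section 1.1 gives an HbA1c at or below target as the reason the problem goes unrecognised.

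**Consequences without a listed measure.** Section 1.1 names four consequences: distress, recurrent hypoglycaemia, eroded awareness and healthcare use. Only the first two have a listed measure. The primary objective asks how problematic the fear is, and the study makes one survey contact with no follow-up outside usual care. An item left out could not be recovered for non-Imperial participants.

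**Working it through.** **1. Source by group, from the text**

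| Group | HbA1c and complications | Where stated |
|---|---|---|
| Imperial, consenting | Health record (biochemistry and medical history) | Section 6 |
| Non-Imperial | Not stated expressly; the survey is the only route left | Section 3.1, source line |

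The gap is therefore one missing line for one of two groups. Appendix 2 (data flow mapping) might hold it, but its content is not in the text available.

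**2. Consequences against listed measures**

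- Distress: PAID-5, with PHQ-9 and GAD-7 alongside.
- Recurrent hypoglycaemia: hypo frequency and severity.
- Hypoglycaemia awareness: not listed in Section 3.1 or Appendix 1.
- Healthcare use: not listed in either place.

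So 2 of 4 are not listed. That is not the same as not collected, because the survey itself is not shown.

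**3. Illustrative size of the source problem**

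The plan gives no figure to reproduce: 350 is an upper limit with no power calculation behind it. The assumptions, none from the documents, are:

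- non-Imperial share f = 0.1 to 0.4
- HbA1c SD 13 mmol/mol (variance 169)
- self-report error SD e = 5 to 8 mmol/mol
- difference between sources d = 3 to 6 mmol/mol
- difference between groups on the Hyperglycaemia Avoidance Scale D = 0.2 to 0.5 SD

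Correlation serves only as a common scale. Section 7 names proportions tests, chi-squared tests, t-tests and ANOVAs.

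*(i) HbA1c missing for the non-Imperial group.* The smallest correlation detectable with 80% power at two-sided 5% is tanh(2.802/√(n−3)).

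- n = 350: tanh(2.802/√347) = 0.149
- f = 0.1, n = 315: tanh(2.802/√312) = 0.157
- f = 0.4, n = 210: tanh(2.802/√207) = 0.192

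*(ii) HbA1c self-reported with random error.* The pooled attenuation factor is √[169/(169 + f·e²)].

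- f = 0.1, e = 5: √(169/171.5) = 0.993, a loss of 0.7%
- f = 0.4, e = 8: √(169/194.6) = 0.932, a loss of 6.8%

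*(iii) The sources also differ systematically, with no true association within either group.* The spurious r is f(1−f)·d·D / √[(169 + f(1−f)d²)(1 + f(1−f)D²)].

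- f = 0.1, d = 3, D = 0.2: 0.054/√(169.81 × 1.0036) = 0.004
- f = 0.3, d = 6, D = 0.5: 0.63/√(176.56 × 1.0525) = 0.046
- f = 0.4, d = 6, D = 0.5: 0.72/√(177.64 × 1.06) = 0.052

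The largest value is about a third of the detectable correlation at n = 350 (0.052/0.149 = 0.35).

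**The case for a change.** The best case for a change is that it would be cheap: a line on source, a source variable, a few survey questions and an Imperial-only sensitivity analysis. One contact is planned, and the protocol does not say whether self-reported and record values will be pooled or flagged. A small spurious correlation is also not quite nothing to a significance test. At the most adverse corner above, 0.052 × √347 = 0.97, and a true null would reject with probability of about 16% instead of 5% (normal approximation). That corner needs a 40% non-Imperial share, a 6 mmol/mol shift between sources and a half-SD difference in avoidance scores, all together and all assumed.

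What stands is that the protocol would be clearer with an explicit line for non-Imperial participants. The rest is weaker:

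- The missing-data reading sets aside the survey route that Section 3.1 names for the whole list.
- Imperial status is needed for record linkage, so the team knows who had record review. An Imperial-only check can be run without amending anything.
- Adjusting for source would add little. Source and recruitment group nearly coincide, so a model could not separate them.
- The interview sample needs only a spread of HbA1c, for which a self-reported value is good enough.

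On awareness and healthcare use, the clinical-factors objective is worded openly and could take them in, and they would be reasonable additions. But Section 1.1 is background, and no objective commits the study to measuring every association it mentions. Nor would the primary answer rest on distress and hypoglycaemia alone. Section 3.1 also lists the Hyperglycaemia Avoidance Scale, HFS-II, PHQ-9, GAD-7, trait anxiety, HbA1c and complications, and about 16 interviews explore the fear directly.

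**Conclusion.** No change follows. The first point is a gap that the team would fill sensibly through the survey route the protocol already names, and no wrong result has been shown to follow from it. If the survey supplies the non-Imperial values, the illustrated effects are small: attenuation of 0.7-6.8% and a spurious correlation of 0.004-0.052. Even if those values were missing, the detectable correlation would rise only from 0.149 to between 0.157 and 0.192. All of these figures rest on assumed inputs. The true size is unknown because the non-Imperial share is not stated.

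The second point is a preference about scope. Two of the four consequences named in the background have no listed measure, but no objective names them and the unseen survey may already ask about them. This conclusion rests on reading the Section 3.1 source line as covering HbA1c and complications for non-Imperial participants, which is its natural sense.

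### The automatic GP letter uses PHQ-9 item 9 alone only at its top score, and the plan does not say who reads an answer of 1 or 2

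*Combined protocol and SAP*

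**What the plan says.** Section 6 (Assessment and Follow-up) gives three score triggers: GAD-7 in 15-21, PHQ-9 in 20-27, "or who scores 3 on question 9 of the PHQ-9 (this question relates to thoughts of harm to self"). A participant who meets any of them "will have a letter sent to their GP advising them of this, and the participant will receive a copy".

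The next paragraph of section 6 adds two routes with no score threshold:
- A disclosure to the researchers that amounts to a safeguarding issue "or a potential risk to self or others, will be shared with the clinical team". It is then handled through the normal care pathway, and outside agencies can be brought in if needed.
- "Where participants report mental health problems such as anxiety or depression", the Clinical Psychologist judges whether to signpost or refer. The examples given include local mental health access points.

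The description of the interview sub-study adds risk management for disclosures made during interviews.

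Forms can be completed online, on paper that "will be sent by post for completion at home", or in clinic with the option of taking them home. Recruitment includes "Participants with type 1 diabetes who do not attend an Imperial College Healthcare NHS Trust diabetes clinic" if they have agreed to research contact. Section 6 also states: "No follow up outside of usual care will be provided".

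**The concern.** Item 9 is the one question that the protocol itself singles out as being about self-harm. Yet any non-zero answer below the top one affects the letter only through the PHQ-9 total. Someone can report some thoughts of self-harm, stay under both severe totals, and meet no score trigger.

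What happens next then depends on whether staff regard a mark on a returned form as a disclosure. Because the rule names a 3, staff could reasonably take it that 1 and 2 need nothing further. Many forms will be completed with no clinician present, so there may be no conversation in which the same worry would come up. What is at stake is participant safety; no objective or estimate of the study is affected.

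**Working it through.** **Inputs, all from section 6.** GAD-7 trigger 15-21; PHQ-9 trigger 20-27; item 9 trigger 3. The questionnaires are attached separately and were not available, so the item range has to be inferred.

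**Item range.** Assuming equally scored items, the maximum per item is 27 / 9 = 3 for the PHQ-9. The GAD-7 gives the same value: 21 / 7 = 3. A score of 3 on item 9 is therefore its top answer, and 1 and 2 are the other two non-zero answers.

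**What the PHQ-9 total needs.** The other eight items have a maximum of 8 x 3 = 24. To reach a total of 20 they must sum to at least 20 minus the item 9 score:

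| Item 9 | Other eight must reach (of 24) | PHQ-9 totals with no letter, if GAD-7 is under 15 |
|---|---|---|
| 0 | 20 | 0-19 |
| 1 | 20 - 1 = 19 | 1-19 |
| 2 | 20 - 2 = 18 | 2-19 |
| 3 | no minimum; item 9 is enough | none |

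**Worked pair.** Item 9 = 2 and other items 17 gives PHQ-9 = 19; with GAD-7 = 14 there is no letter. Item 9 = 0 and other items 20 gives PHQ-9 = 20, and a letter is sent.

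**Do the other provisions settle what happens to a 1 or 2?**
- *Disclosure route.* It has no threshold and does not exclude written answers, but it does not say that a questionnaire answer is a disclosure.
- *Psychologist's judgement.* It could apply, but it is not tied to item 9, and nothing says that the psychologist sees each form.
- *Interview safeguards.* These reach about 16 of up to 350 participants (16 / 350 = 4.6%), chosen for fear or avoidance of hyperglycaemia.
- *Handling of returned forms.* Section 6 describes recording, storing and downloading the data. It gives no step at which someone reads item 9 on receipt, and no time limit.

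**The case against.** The strongest reply is that section 6 works in two layers: an automatic letter at fixed scores, and clinical judgement for everything else. Questionnaire answers are participants' own reports returned to the research team, so it is natural to read the second layer as including them. This largely stands. A reader might infer that a participant who answers 1 or 2 gets no action and that no clinician will be told. The documents do not support that, because both judgement routes could cover the answer. What they lack is a statement that the routes do cover it, and a person assigned to look.

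A reader might also infer that participants from outside the Imperial clinics have nowhere to be directed. That goes too far as well. The disclosure sentence allows other agencies to be contacted, and the signposting examples are not limited to Imperial patients. No contact is named for this group, which is a smaller gap.

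It is also fair to say that any cut-off produces boundary pairs like the one above, that the wording of answers 1 and 2 cannot be seen, and that the study has ethics approval. Nothing in the documents shows that 3 is the wrong point for an automatic letter, and this point does not ask to move it. The participant information and the data flow appendix, whose content is not shown, may add detail on who reads the forms. The score rule itself is stated in full in section 6.

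The sentence saying that "GPs will not be informed of their participation in the study as it will not affect their care" sits awkwardly beside the letter rule, but a general statement and a specific exception can be reconciled. That is a tidy-up only.

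**Conclusion.** The point holds in a limited form. By score, two of the three non-zero answers to item 9 lead to nothing unless PHQ-9 reaches 20 or GAD-7 reaches 15. The routes that could deal with these answers rest on an unstated reading of what counts as a disclosure and on someone happening to read the item. Staff could follow the score rule exactly and leave such an answer unreviewed, although the judgement routes would allow them to act on it.

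The number of participants affected is unknown: the documents give no rate for these answers, and 350 is a ceiling on enrolment. The conclusion assumes items scored 0 to 3 and rests on the visible text. It is a cheap improvement for patient safety and does not bear on the validity of the analysis.

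**What to change.** Keep the automatic letter at item 9 = 3 and at the two severe totals. Add to the same part of section 6, in words such as: *The Clinical Psychologist will review every non-zero answer to PHQ-9 item 9 promptly on receipt, treat it as a possible disclosure of risk, and choose among a GP letter, the clinical team, other agencies, and signposting or referral. Where the participant has no Imperial clinical team, the GP will be the contact.* The sponsor should set the interval that counts as prompt. As a tidy-up, add an exception for these letters to the sentence about GPs not being told of participation.

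The cost is a few sentences, a matching line in the participant information, and at most about 350 single-item checks over 9 months. Some reviews will need no action. Participants told of the review may answer item 9 less candidly, which is the main trade-off to weigh.
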